10.3 Sample Size Justification

For an alpha of 0.05 and a power of 80%, 48 subjects per group allow detection of a 30% difference in the incidence of oral mucositis (range of oral mucositis is 25% to 50%). Efficacy assessment will occur at study completion.

Twenty subjects per group can detect a 0.6 unit difference in the toxicity scale. This is based on an effect size of 0.90 and a SD of 0.66 units. This is a medium sized clinical difference using Cohen's criteria. This study will serve as a pilot for a larger study. For toxicity, which can only be estimated in the treatment group, 48 subjects in the Caphosol group will allow estimation of a 95% confidence interval of the toxicity of about $\pm 15\%$. Assessment of toxicity will occur once the study enrolls 20 patients to each arm to obtain a preliminary estimate (95% CI) for toxicity and again at study completion (to obtain a more precise estimate). While the study is stopped if it passes the sequential boundary, to obtain an estimate of the toxicity and its 95% Confidence interval (95% CI) both an interim analysis and an analysis at the end of the study will be used to estimate the 95% CI – most precisely at the end of the study.

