1.0 BACKGROUND

Mucositis in Children, Adolescents and Young Adults Undergoing Chemotherapy

Oral mucositis, a common and debilitating complication of cancer therapy, is an inflammatory injury to the epithelial and sub-epithelial cells of the oral mucosa. Oral mucositis is thought to develop according to a five-stage model: 1) initiation; 2) up-regulation with generation of messengers; 3) signaling and amplification 4) ulceration with inflammation; and 5) healing, and typically develops 7-14 days into a chemotherapy course (1).

The incidence and severity of oral mucositis depends on many factors including the age and diagnosis of the patient, the specific treatment regimen, underlying oral hygiene and genetic factors (2-4). The incidence of oral mucositis in patients receiving chemotherapy ranges from around 40% of patients receiving myelosuppressive chemotherapy for solid tumors to 70-90% of patients receiving myeloablative therapy prior to stem cell transplant (1, 5, 6). A commonly used grading scale for mucositis is the Common Terminology Criteria for Adverse Events (CTCAE version 4.0) grading scale, where grading is based on both subjective and objective assessments on a 5 point scale (Grade 1 to Grade 5).

Adverse Event	1	2	3	4	5
Mucositis Oral Definition: A disorder characterized by inflammation of the oral mucosal.	Asymptomatic or mild symptoms; intervention not indicated	Moderate pain; not interfering with oral intake; modified diet indicated	Severe pain; interfering with oral intake	Life-threatening consequences; urgent intervention indicated	Death

From the Common Terminology Criteria for Adverse Events (CTCAE) Version 4.0 Published: May 28, 2009 (v4.03: June 14, 2010) U.S. DEPARTMENT OF HEALTH AND HUMAN SERVICES National Institutes of Health National Cancer Institute, p. 19

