3.2 Exclusion Criteria

- a. Patients receiving glutamine treatment for oral mucositis.
- b. Patients undergoing autologous or allogeneic hematopoietic cell transplantation are excluded from this study.
- c. Patients receiving concurrent Head & Neck radiation therapy or within 6 weeks of completion of radiation therapy.
- d. Pregnant or lactating patients. The agent used in this study is not known to be teratogenic to a fetus, but has not been studied, and there is no information on the excretion of the agent into breast milk. All females of childbearing potential must have a blood test or urine study within 2 weeks prior to registration to rule out pregnancy.
- e. Known allergy to Caphosol

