10.2 Statistical Analysis

Comparisons of binary outcomes such as prevention of oral mucositis will use logistic analysis or Fisher's exact test if the numbers are small. Comparisons of the severity of oral mucositis (an ordinal scale) will use the Wilcoxon rank sum test since the data is on a 5 point Likert scale, although there are really only two levels of values. Similarly for the secondary outcome an ordinal pain scale can be treated as an ordinal scale. Length of stay and duration of TPN will use a t-test plus a log transform, if necessary to reduce the skewness of the data. Otherwise the Wilcoxon test will be used.

Although there may be loss to follow-up, we don't expect it because continued

chemotherapy depends on the clearing of the mucositis.

The primary analysis for mucositis will be based on a binary scale (Grade 1 versus Grade ≥ 2 mucositis) because the mucositis essentially has only two clinically pieces to the scale. It also represents common clinical practice.

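### Does Section 10.3 contradict itself by pairing a 30-point detectable difference with a mucositis range only 25 points wide?

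*Combined protocol and SAP*

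**What the plan says.** Section 10.3 (Sample Size Justification) holds the only power statement for the primary endpoint. It opens with "For an alpha of 0.05 and a power of 80" (per cent) and continues that "48 subjects per group allow detection of a 30% difference in the incidence of oral mucositis (range of oral mucositis is 25% to 50" (per cent, where the bracket closes). It gives no pair of arm rates. It does not say which arm the range describes, whether the difference is absolute or relative, or whether the test is one- or two-sided.

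Section 10.2 (Statistical Analysis) defines the endpoint: "The primary analysis for mucositis will be based on a binary scale (Grade 1 versus Grade ≥ 2 mucositis"). For the test, it says that binary outcomes "will use logistic analysis or Fisher's exact test if the numbers are small".

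Two other places bear on plausible rates. Section 1.0 (Background) says that incidence under chemotherapy "ranges from around 40% of patients receiving myelosuppressive chemotherapy for solid tumors to 70-90% of patients receiving myeloablative therapy prior to stem cell transplant". Section 3.2 (Exclusion Criteria) says: "Patients undergoing autologous or allogeneic hematopoietic cell transplantation are excluded from this study".

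**The concern.** The two numbers in the same sentence do not obviously fit. The widest gap inside the range is 50 − 25 = 25 points, short of 30. If the range is instead the control incidence, a control rate below 30% cannot fall by 30 points: from 25% it would have to reach −5%.

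If the authors really had 50% against 25% in mind, 48 per group would be too few for a two-sided test, and the chance of missing that effect would be 28% instead of the planned 20%. A reader of a null result also could not tell which effect the trial was sized to find.

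**Working it through.** **Inputs.** From Section 10.3: alpha 0.05, power 80%, n = 48 per group, difference d = 0.30, range 0.25 to 0.50. Assumption: two-sided test, so z = 1.960; for 80% power z = 0.842. Section 10.2 expects no loss to follow-up, so n is not inflated.

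**Formulas.** With p̄ the mean of the two rates:

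- n = [1.960·√(2p̄(1−p̄)) + 0.842·√(p₁(1−p₁)+p₂(1−p₂))]² / d²
- Continuity-corrected n = (n/4)·[1 + √(1 + 4/(n·d))]²
- Power at 48 = Φ{[d·√48 − 1.960·√(2p̄(1−p̄))] / √(p₁(1−p₁)+p₂(1−p₂))}
- Fisher power: full enumeration of all outcomes with 48 and 48.

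**Step 1: reproduce the plan's 48.** Take 25% as the lower rate and add 30 points: 55% against 25%.

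- p̄ = 0.40; √0.48 = 0.6928; √(0.2475 + 0.1875) = 0.6595.
- n = (1.3579 + 0.5551)² / 0.09 = 40.7.
- Corrected n = (40.66/4)·(1 + √1.3279)² = 47.1, which rounds up to 48.
- Power at 48: (2.0785 − 1.3579)/0.6595 = 1.09, so 86%; Fisher 81%.

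**Step 2: other 30-point gaps.**

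| Rates | n per group (corrected) | Power at 48 (Fisher) |
|---|---|---|
| 60% v 30% | 42.0 (48.4) | 85% (80%) |
| 65% v 35% | 42.4 (48.8) | 85% (80%) |
| 70% v 40% | 42.0 (48.4) | 85% (80%) |
| 75% v 45% | 40.7 (47.1) | 86% (81%) |
| 80% v 50% | 38.5 (44.9) | 88% (83%) |
| 50% v 20% | 38.5 (44.9) | 88% (83%) |
| 45% v 15% | 35.4 (41.8) | 91% (87%) |
| 40% v 10% | 31.5 (37.9) | 94% (91%) |
| 35% v 5% | 26.7 (33.0) | 97% (96%) |

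Over all 30-point gaps the lowest power is 84.8% (at about 65% v 35%); the lowest Fisher power is 79.9%.

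**Step 3: the reading that falls short.** 50% against 25%, d = 0.25, p̄ = 0.375.

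- Two-sided: (1.7321 − 1.3419)/0.6614 = 0.59, so 72% (Fisher 64%); 80% power needs 58 per group (66 corrected).
- One-sided 0.05: (1.7321 − 1.1262)/0.6614 = 0.92, so 82%; 80% power needs 46 per group.

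**Step 4: 30% as a relative reduction.** 50% to 35% has 32% power at 48 and needs 170 per group. This is nowhere near the stated 48, so the absolute reading is the one the calculation supports.

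**The case for a change.** The strongest case for acting is that neither reading that keeps to the range fits well. As the control rate, the most natural reading in a prevention trial, it rules out a 30-point fall at its lower end, and above that end power exceeds the stated 80%. As the two arm rates, it leaves a two-sided test short. The reading that reproduces 48 makes 25% to about 45% the Caphosol rate, with control at 55% to 75%. That lies above the roughly 40% that Section 1.0 gives for solid-tumor chemotherapy, and the higher background figure there concerns transplant patients, who are excluded. Section 10.3 also calls the study a pilot for a larger one, so its assumptions may be reused.

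Part of this stands. The section does leave the rates, the meaning of the range, the sidedness and the test unstated, and a 30-point fall is impossible from a control rate below 30%.

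The rest does not establish an error. Power above 80% is no misfit, because the sentence claims only that the sample can "allow detection of a 30% difference in the incidence of oral mucositis". The background figure of about 40% is a weak limit: it carries no grade and covers solid tumors, whereas the trial enrols by listed agents that the Synopsis and Appendix 1 describe as carrying a high incidence. Treatment and evaluation also recur at every eligible chemotherapy course (Sections 5.4 and 5.5), so per-patient incidence could exceed a per-course figure. The documents neither establish nor exclude control rates of 55% to 75%.

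**Conclusion.** No change to the plan follows. The claim that 48 per group gives 80% power for a 30-point difference is met to within rounding: at least 84.8% by the normal approximation and 79.9% by Fisher's exact test, whatever the two rates. The apparent contradiction depends on the unstated premise that both arms lie between 25% and 50%, and the 72% figure depends on a two-sided test as well.

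These results assume an absolute difference, a two-sided 0.05 test except where noted, no loss to follow-up and a single final analysis. The O'Brien-Fleming interim look in Section 10.1 costs only about half a percentage point of power (final critical value about 1.977).

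What is left is incomplete documentation of the planning assumptions. An analyst can work from the stated n and report the observed difference with its confidence interval, which will show what a null result excludes. Writing the assumptions down would leave the enrolment, the primary comparison and every result as they are.

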4.3 RANDOMIZATION PLAN

The randomization procedure will be based on creating a block for every 4 subjects with 2 subjects of each treatment randomly positioned in the block. Withdrawal is covered in section 5.5. This should provide balance among the two arms for rates of mucositis by disease. If imbalance exists after randomization, covariates will be used for adjustment of the results.

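### Section 10.3 calls a detectable toxicity difference of about 0.9 SD medium when it is large, and leaves unclear whether toxicity is compared between arms or estimated in one

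*Combined protocol and SAP*

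**What the plan says.** Section 10.3 (Sample Size Justification) opens with the mucositis incidence endpoint: "For an alpha of 0.05 and a power of 80%, 48 subjects per group" are said to allow detection of a 30% difference. It then turns to toxicity and claims: "Twenty subjects per group can detect a 0.6 unit difference in the toxicity scale". The inputs behind that claim come next: "This is based on an effect size of 0.90 and a SD of 0.66 units". The plan then labels the result, naming Cohen's criteria as its standard: "This is a medium sized clinical difference". The toxicity sentences state no alpha, power or sidedness, and Section 10.3 does not define the scale.

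Two sentences after the label, the paragraph takes a one-arm view. "For toxicity, which can only be estimated in the treatment group" introduces a 95% confidence interval of about ±15% from the 48 Caphosol subjects. The assessment at 20 patients per arm is described as giving a preliminary estimate with a 95% CI, and no interval width is stated for it.

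Section 10.1 takes the two-arm view: safety and tolerance rest on the differential incidence of severe adverse events, and a sequential boundary is set on the difference in adverse events. Section 5.0 has the diary record side effects attributed to Caphosol in the Caphosol arm only.

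**The concern.** The plan names a yardstick and then misapplies it. Under Cohen's usual benchmarks for a standardised mean difference (0.2 small, 0.5 medium, 0.8 large; a textbook convention that the plan invokes without printing the cut-offs), an effect of 0.90 is above the large threshold. Read at face value, the label credits 20 per group with sensitivity to moderate toxicity differences that it does not have.

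The second difficulty is which quantity the 20-per-arm figure supports. A detectable difference between groups needs an estimate in both. A statement that toxicity is estimable in one arm only does not fit with it, or with the differential adverse-event comparison in Section 10.1. Tolerability is a primary objective (Section 2.1), so those who monitor the trial should be able to tell whether the 20-per-arm assessment is a comparison or a one-arm estimate, and how precise it is.

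**Working it through.** **Inputs.** From Section 10.3: n = 20 per group, difference 0.6 units, effect size 0.90, SD 0.66. From Section 4.3: 1:1 allocation ("creating a block for every 4 subjects with 2 subjects of each treatment randomly positioned in the block"). Alpha 0.05 and power 80% are borrowed from the incidence sentence of Section 10.3. Two-sided testing is assumed.

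**Step 1: are the plan's figures consistent?** 0.6 / 0.66 = 0.909, and 0.90 × 0.66 = 0.594. They agree to rounding.

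**Step 2: reproduce 20 per group.** Normal approximation: n = 2(1.96 + 0.842)² / d² = 15.70 / d².
- d = 0.90: 15.70 / 0.81 = 19.4, so 20. The noncentral t gives 20.4.
- d = 0.909: 15.70 / 0.826 = 19.0. The noncentral t gives 20.0.
- Power at 20 per group by t-test: 79.2% for d = 0.90 and 80.0% for d = 0.909.
- A one-sided test would need about 16 per group, so two-sided is the variant that matches the plan.

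The plan's 20 is reproduced. The smallest effect detectable with 80% power at 20 per group (t-test) is d = 0.909, or 0.909 × 0.66 = 0.60 units.

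**Step 3: power for a medium effect.** d = 0.5 corresponds to 0.5 × 0.66 = 0.33 units. In the normal approximation, power = Φ(d√(n/2) − 1.96). At n = 20 this is Φ(0.5 × 3.162 − 1.96) = Φ(−0.379) = 35.2%.

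| n per group | Test | Power at d = 0.5 |
|---|---|---|
| 20 | two-sided t | 33.8% |
| 20 | two-sided, normal approximation | 35.2% |
| 20 | one-sided t | 46.3% |
| 48 | two-sided t | 67.9% |

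For 80% power at d = 0.5, n = 15.70 / 0.25 = 62.8, so 63 per group (64 by t-test). That exceeds the planned 48.

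**Step 4: one-arm precision.** Half-width = 1.96√(p(1 − p)/n).

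| Toxicity rate p | n = 20 | n = 48 |
|---|---|---|
| 50% (worst case) | ±21.9 points | ±14.1 points |
| 25% | ±19.0 | ±12.3 |
| 10% | ±13.1 | ±8.5 |

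The plan's ±15% at n = 48 is about right as a worst case. At n = 20 with no events, the exact 95% upper limit is 1 − 0.025^(1/20) = 16.8%.

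**Step 5: the statements side by side.** Section 10.3 first sizes a two-group difference, then calls toxicity estimable in one arm. Section 10.1 compares adverse events between arms. Section 5.0 collects Caphosol-attributed side effects in one arm. The last fits a one-arm rate; the first and third need both arms.

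**The case against.** The best defence is that only an adjective is wrong. The effect size of 0.90 is printed in the sentence before the label, the four figures agree, and the plan nowhere claims power at d = 0.5. That stands as far as the arithmetic goes. It does not rescue the label, which cites a named criterion and gets it wrong.

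A reader might infer that a null result at 20 per arm would be taken to rule out medium toxicity, so that two in three such differences would be missed at the first safety look. The documents do not support this. The 20-per-arm assessment is described as a confidence-interval estimate with no test or decision rule attached. Stopping is assigned to the sequential boundary, alongside the reporting and committee review in Sections 8.3 and 9.3. Nor is it shown to come first: Section 10.1 sets an adverse-event analysis at the end of month 3. With uniform accrual of 96 patients over the synopsis's 6 to 8 months (an assumption), 36 to 48 would be enrolled by then, against the 40 needed for 20 per arm.

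A reader might also infer that the plan declares toxicity impossible to compare between arms. Its wording concerns estimation, and Section 5.0 offers a partial reconciliation, since a Caphosol-attributed rate is naturally one-arm. But Section 10.3 does not limit the statement in that way, and as written it does not fit the two-group sizing or Section 10.1.

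Finally, ±22 points is a worst case, and Sections 7.1.7 and 8.2 expect no toxicity. That is fair, and is why a range is shown.

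**Conclusion.** The point holds as a correction of wording and consistency. The detectable toxicity difference is large by the criteria the plan cites. Power for a medium difference is about 34% at 20 per group and about 68% at 48 per group, two-sided at 0.05; at 20 per group it is about 46% one-sided. These figures assume that the alpha stated for incidence carries over, and they take the SD of 0.66 as given on a scale that Section 10.3 does not define. It follows that the text does not settle whether that scale and the one-arm percentage measure the same thing.

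The one-arm statement needs to be reconciled with the two-group sizing beside it and with Section 10.1. It would be wrong to conclude that the sample size is miscalculated: 20 per group is right for the effect stated, and the 96 patients are justified by mucositis incidence.

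**What to change.** Make three edits to Section 10.3:

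1. Describe the 0.6-unit difference as large (d about 0.9). Add that power at 20 per group for d = 0.5 (0.33 units) is about 34%, and state the alpha, sidedness and test that this assumes.
2. Replace the one-arm statement with one that covers only side effects attributed to Caphosol, which Section 5.0 collects in that arm alone. Say that adverse events are compared between arms as in Section 10.1. Deleting one of the two conflicting sentences would not be enough, because Section 10.1 would still have to be matched.
3. Because the 20-per-arm assessment is a confidence-interval estimate, give its one-arm precision beside the n = 48 figure: half-width up to about 22 points at a 50% rate and about 13 points at 10%, against about 14 and 8.5 points at n = 48.

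The cost is wording only. The stated sensitivity to toxicity becomes less favourable; patient numbers, data collection and the stopping boundary are untouched.

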11.0 CONDUCT OF THE STUDY

11.1 Good Clinical Practice

The study will be conducted in accordance with the appropriate regulatory requirement(s). The investigator will be thoroughly familiar with the appropriate use of the drug as described in the protocol. Essential clinical documents will be maintained to demonstrate the validity of the study and the integrity of the data collected. Master files should be established at the beginning of the study, maintained for the duration of the study and retained according to the appropriate regulations.

11.2 Ethical Considerations

The study will be conducted in accordance with ethical principles founded in the Declaration of Helsinki. The IRB will review all appropriate study documentation in order to safeguard the rights, safety and well-being of the patients. The study will only be conducted at sites where IRB approval has been obtained. The protocol, informed consent, written information given to the patients, safety updates, annual progress reports, and any revisions to these documents will be provided to the IRB by the investigator.

For patients 16 years of age and older:

[figure not shown]
Karnofsky Performance Scale	
Percent	Description
100	Normal, no complaints, no evidence of disease.
90	Able to carry on normal activity; minor signs or symptoms of disease.
80	Normal activity with effort; some signs or symptoms of disease.
70	Cares for self, unable to carry on normal activity or to do active work.
60	Requires occasional assistance, but is able to care for most of his/her needs.
50	Requires considerable assistance and frequent medical care.
40	Disabled, requires special care and assistance.
30	Severely disabled, hospitalization indicated. Death not imminent.
20	Very sick, hospitalization indicated. Death not imminent.
10	Moribund, fatal processes progressing rapidly.
0	Dead

For patients less than 16 years of age:

Lansky Performance Scale	
Lansky Score	Play Score
100	Fully active, normal
90	Minor restrictions in physically strenuous activity
80	Active, but tires more quickly
70	Both greater restriction of and less time spent in play activity
60	Up and around, but minimal active play; keeps busy with quieter activities
50	Gets dressed but lies around much of the day, no active play but able to participate in all quiet play and activities
40	Mostly in bed; participates in quiet activities
30	In bed; needs assistance even for quiet play
20	Often sleeping; play entirely limited to very passive activities
10	No play; does not get out of bed
0	Unresponsive

APPENDIX 3
Pain Assessment Scales

Wong-Baker FACES Pain Rating Scale

- 0 = Very Happy, No Hurt
- 1 = Hurts Just a Little Bit
- 2 = Hurts a Little More
- 3 = Hurts Even More
- 4 = Hurts a Whole Lot
- 5 = Hurts as Much as You Can Imagine (Don't have to be crying to feel this much pain)

Explain to the person that each face is for a person who feels happy because he has no pain (no hurt) or sad because he has some or a lot of pain. Face 0 is very happy because he doesn't hurt at all. Face 1 hurts just a little bit. Face 2 hurts a little more. Face 3 hurts even more. Face 4 hurts a whole lot. Face 5 hurts as much as you can imagine, although you don't have to be crying to feel this bad. Ask the person to choose the face that best describes how he is feeling.

Pain Rating scale is recommended for subject's age 3 years and older.

Brief Word Instructions: Point to each face using the words to describe the pain intensity. Ask the child to choose face that best describes own pain and record the appropriate number.

Likert 0-10 Numeric Pain Rating Scale
